After three patients in a dose cohort, or six patients in an expanded dose cohort, complete the 21-day dose-limiting toxicity assessment period, the incidence of dose-limiting toxicity, treatment-related safety observations and other available data, such as pharmacokinetic data, will be reviewed by the Sponsor Medical Monitor, Sponsor and Investigators. If no patient in a three-patient cohort or no more than one patient in a six-patient dose cohort experiences treatment-related dose-limiting toxicity, the dose level will be deemed safe and dose escalation may proceed unless there are other unsuspected but concerning safety observations that suggest either an expansion of the current dose level or implementation of an intermediate dose level.

After completion of Cycle 6, doxorubicin will be discontinued as per standard of care to avoid development of cumulative cardiac toxicity. Thereafter, beginning with Cycle 7, TTI-621 will be administered as monotherapy on Day 1 and Day 15 of 28-day cycles until documentation of disease progression or unacceptable toxicity.

Objective disease assessments will be performed after every second cycle of treatment for approximately 50 weeks and after every third cycle thereafter. A patient enrolled in an expansion cohort who withdraws or is withdrawn from the study prior to completion of two cycles of treatment and objective disease assessment after the second cycle for a reason other than disease progression or safety will be replaced in order to meet the statistical criteria for the Simon two-stage study design. Patients who withdraw from the study without objective evidence of disease progression will be followed until documentation of disease progression or initiation of another treatment. All patients will be followed in the Long-Term Follow-Up period for survival.

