- An intercurrent illness or change in the patient's condition that renders the patient unsuitable for further treatment in the opinion of the Investigator; exception may be made for patients in whom the intercurrent illness or change in condition is thought to render the patient ineligible for continued treatment with doxorubicin despite optimal prophylaxis and medical support and the patient has received at least four cycles of doxorubicin and is receiving clinical benefit and the investigator feels, with Sponsor Medical Monitor concurrence, that continuation with TTI-621 monotherapy would be reasonable and the patient meets criteria for TTI-621 re-treatment as described in [Section 9.2.2](#)
- Significant non-compliance with protocol
- Pregnancy
- Withdrawal of consent (patient may participate in long-term assessment of survival and disease status [if withdrawn prior to documentation of objective disease progression] if consent for this portion of the study is not withdrawn)
- Subject is lost to follow-up
- Termination of the study by the sponsor

At the investigator's discretion and in agreement with the Sponsor Medical Monitor, treatment after objective disease progression may continue for a patient who is clinically stable and receiving meaningful clinical benefit and the investigator feels it is in the patient's best interest to continue treatment. The reason for continuing treatment must be thoroughly discussed, agreed with the Sponsor Medical Monitor, and clearly documented in the study files.

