#### 12.1.2. Expansion Cohorts

Expansion cohorts are planned to evaluate two TTI-621 dose levels in combination with doxorubicin: a low dose of TTI-621 (Cohort A) and a higher dose (Cohort B). A Simon two-stage design will be used for each dose cohort, assuming a baseline overall response rate of 10% with doxorubicin monotherapy. In the Simon two-stage design and an alternative of 25%, a power of 90% and one-sided Type 1 error set at 0.20, each dose level cohort will require 18 patients enrolled and evaluable for response in Stage 1; with at least two clinical responses, an additional 13 patients will be enrolled in Stage 2. The combination will be considered worthy of further study if at least five clinical responses are observed in either 31-patient cohort.

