### 12.2. Analysis Populations

The following analysis populations are defined for the study:

**Safety population:** all patients who received at least 1 dose of TTI-621

**Efficacy population:** all patients who received at least 1 dose of TTI-621

**DLT-evaluable population:** all patients who received the full dose of doxorubicin and the planned doses of TTI-621 on Day 1 and Day 8 and have been followed for the entire 21-day DLT period (i.e., Cycle 1) or who have a DLT during Cycle 1 will be considered DLT-evaluable

**Response-evaluation population for Simon two-stage design:** all patients in either Expansion Cohort A (low dose TTI-621) or Expansion Cohort B (high dose TTI-621) who complete at least two cycles of treatment as described in the protocol and have a post-treatment objective disease assessment unless they were withdrawn prior to meeting this criterion for safety or earlier demonstration of objective disease progression

**CCI** [REDACTED]: all patients who received at least one dose of TTI-621 and have at least one evaluable blood sample for analysis collected

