**12.3.3. Clinical Benefit**

Clinical efficacy will be evaluated by tumor response for patients with measurable disease as assessed by the Investigators using RECIST v1.1 (Appendix B). Duration of response will be calculated for patients who achieve a CR or PR and is defined as the time from the date of first documented response (CR or

PR) to the date of documented progression or death after achieving response. Disease control rate is defined as the percentage of patients who have achieved CR, PR, or SD lasting at least 12 weeks.

Clinical activity based on CCI [REDACTED] will be assessed as an CCI [REDACTED] of the study.

Patients enrolled in an expansion cohort who withdraw from the study prior to the first objective disease assessment for a reason other than disease progression or safety will be replaced in order to meet the statistical criteria for the Simon two-stage design; these patients will not be included in the response-evaluable population. For a patient enrolled into the dose expansion portion of the study based on local pathology that is not confirmed during central review, the patient must be replaced for purposes of meeting the statistical requirements of the study but may be allowed to continue on treatment after discussion with the Sponsor Medical Monitor.

For patients with asymptomatic progression only or suspected pseudoprogression, the patient may continue treatment beyond progression until a confirmation scan at least four weeks later has confirmed progression.

Efficacy analyses will be based on the efficacy analysis population, i.e. all patients who received at least one dose of study treatment, unless otherwise specified.

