CR, complete response; PD, progressive disease; PR, partial response; SD, stable disease; NE, Not evaluable.

*Evaluation of Best Overall Response When Confirmation of CR and PR Required*

Overall Response First Timepoint	Overall Response Subsequent Timepoint	Best Overall Response
CR	CR	CR
CR	PR	SD, PD or PR a
CR	SD	SD provided minimum criteria for SD duration met, otherwise, PD
CR	PD	SD provided minimum criteria for SD duration met, otherwise, PD
CR	NE	SD provided minimum criteria for SD duration met, otherwise, NE
PR	CR	PR
PR	PR	PR
PR	SD	SD
PR	PD	SD provided minimum criteria for SD duration met, otherwise, PD
PR	NE	SD provided minimum criteria for SD duration met, otherwise, NE
NE	NE	NE

a If a CR is truly met at first timepoint, then any disease seen at a subsequent timepoint, even disease meeting PR criteria relative to baseline, makes this disease PD at that point (since disease must have reappeared after CR). Best response would depend on whether minimum duration for SD was met. However sometimes 'CR' may be claimed when subsequent scans suggest small lesions were likely still present and in fact the patient had PR, not CR at the first time point. Under these circumstances, the original CR should be changed to PR and the best response is PR.

*Timepoint Response: Patients with Non-Target Lesion Assessments*

Non-Target Lesions	New Lesions	Overall Response	Best Response for this Category also Requires
CR	No	CR	Normalization of tumor markers, tumor nodes < 10 mm
Non-CR/non-PD	No	Non-CR/non-PD	
Not all evaluated	No	NE	
Uequivocal PD	Any	PD	
Any	Yes	PD	

Note: Patients with a global deterioration of health status requiring discontinuation of treatment without objective evidence of disease progression at that time should be reported as "symptomatic deterioration". This is a reason for stopping therapy, but is NOT objective PD. Every effort should be made to document the objective progression even after discontinuation of treatment.

*Missing Assessments and Not Evaluable Designation*

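### The rules for who counts in the Simon decision conflict: treated patients who worsen and leave before the first scan can be dropped, and on one reading replaced

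*Protocol*

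**What the plan says.** **Design.** Protocol 12.1.2 plans each expansion cohort "assuming a baseline overall response rate of 10% with doxorubicin monotherapy", with "an alternative of 25%, a power of 90% and one-sided Type 1 error set at 0.20". It states that "each dose level cohort will require 18 patients enrolled and evaluable for response in Stage 1". Two responses open Stage 2 (13 more patients), and five responses among 31 make the combination worthy of further study.

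**Who is in the Simon count.** Protocol 12.2 requires two completed cycles and a post-treatment assessment. Patients who miss this are left out "unless they were withdrawn prior to meeting this criterion for safety or earlier demonstration of objective disease progression".

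**Who is replaced.** The Synopsis (Study Design) says that an expansion patient who leaves early "for a reason other than disease progression or safety will be replaced in order to meet the statistical criteria". Sections 5.1 and 12.3.3 carry the same reasons. Section 12.3.3 adds of the replaced patients that "these patients will not be included in the response-evaluable population".

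**What counts as progression.** Appendix B says of symptomatic deterioration: "This is a reason for stopping therapy, but is NOT objective PD". SAP 8.1 likewise does not accept clinical deterioration as documented progression. Protocol 5.3 lists as its own stopping reason "An intercurrent illness or change in the patient's condition that renders the patient unsuitable for further treatment", separate from radiographic progression and from toxicity.

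**Reported ORR.** SAP 8.2 puts all FAS patients in the denominator, including those with a not-evaluable response. SAP 4.3.2 keeps the counts of 18, 13 and five and the requirement to be evaluable. SAP 6.7 defines only the FAS, SAS and DES, so *evaluable* has no definition in the SAP.

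**The concern.** The population rule and the replacement rule should be complements: an early leaver either counts as a non-responder or is replaced. They are not, because one turns on *objective* progression and the other on progression without that qualifier. A patient who worsens clinically and is never scanned falls between them. So may a patient who withdraws consent while worsening, or who is stopped for a change in condition. Death before the first scan is not named in either rule.

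The go rule is a count, not a rate. If a treated non-responder is swapped for a new patient, the target stays at five while more treated patients have had a chance to respond. In an open-label trial the recorded withdrawal reason would then decide who enters the decision, and the Simon decision and the SAP's all-treated ORR could rest on different patients.

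**Working it through.** **1. The rules side by side, for a treated expansion patient who leaves before the first scan**

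| Reason for leaving | Protocol 12.2 | Synopsis, 5.1, 12.3.3 |
|---|---|---|
| Safety | Counted | Not replaced |
| Radiographic progression | Counted | Not replaced |
| Clinical deterioration, never scanned | Not counted (not objective progression) | Not replaced if read as disease progression; replaced and excluded if progression is read as objective |
| Change in condition or consent withdrawal, not coded as safety or progression | Not counted | Replaced and excluded |

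The third row is the conflict. The fourth is consistent but can remove treatment failures.

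**2. Reproducing the plan's design**

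Inputs from Protocol 12.1.2: p0 = 0.10, p1 = 0.25, 18 patients then 13, continue at ≥ 2, go at ≥ 5 of 31.

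P(go | p) = Σ over x = 2 to 18 of P[Bin(18, p) = x] × P[Bin(13, p) ≥ 5 − x]

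At p = 0.10:
- x = 2: 0.2835 × 0.1339 = 0.0380
- x = 3: 0.1680 × 0.3787 = 0.0636
- x = 4: 0.0700 × 0.7458 = 0.0522
- x ≥ 5: 0.0282
- Sum: **0.182**, within the 0.20 limit

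At p = 0.25: 0.0640 + 0.1488 + 0.2079 + 0.4813 = **0.902**, matching the stated 90%.

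**3. Effect of replacement**

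Let d be the share of treated patients who are non-responders and are excluded and replaced. The documents give no value, so 5 to 20% is an assumption. If the all-treated response rate is 10%, the rate among those counted is p* = 0.10 / (1 − d), and filling 31 places takes 31 / (1 − d) treated patients.

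| d | p* | Treated to fill 31 | P(pass Stage 1) | P(go) |
|---|---|---|---|---|
| 0 | 0.100 | 31.0 | 0.550 | 0.182 |
| 5% | 0.105 | 32.6 | 0.579 | 0.210 |
| 10% | 0.111 | 34.4 | 0.610 | 0.243 |
| 15% | 0.118 | 36.5 | 0.643 | 0.282 |
| 20% | 0.125 | 38.8 | 0.677 | 0.327 |

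Solving P(go) = 0.20 gives d ≈ 3.3% (p* = 0.1034). At that point 31 / 0.967 ≈ 32 patients are treated, that is, about one replacement.

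**4. Exclusion without replacement**

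Dropping a non-responder and not refilling the place leaves the number of responses unchanged against a target of five. It adds no chance of a go. The inflation comes from replacement alone.

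**5. If the benchmark is already an evaluable-patient rate**

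The comparison is then like for like, and step 3 shows no inflation. Counting the leavers as non-responders would instead lower the rate under the alternative to 0.25 × (1 − d). Power falls from 0.902 to 0.874, 0.839, 0.798 and 0.749 at d = 5, 10, 15 and 20%.

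**The case against.** A reader might infer that everyone who leaves early without radiographic progression is dropped, that most are replaced, and that the false-go rate is therefore above 0.20. The documents do not support that.

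- Safety withdrawals stay in the count under 12.2. Under Protocol 13.1.1 a fatal malignancy in the collection period is recorded as a Grade 5 serious adverse event, so some early deaths could be treated as safety.
- Read plainly, the Synopsis, 5.1 and 12.3.3 do not replace a patient who left for clinical progression. Such a patient could be kept as a failure.
- Table 24 (footnote on radiologic assessment) and the Safety Follow-Up Visit in Section 11 call for a scan after removal without radiologic progression. Appendix B asks for every effort to document progression after stopping. A patient who stops treatment for a change in condition may still be scanned. Whether that late scan satisfies 12.2 is not stated.
- The share d is unknown, consent withdrawal has many causes, and nothing says whether the 10% benchmark is an all-treated or an evaluable-patient rate.
- The SAP governs the analysis and reports ORR descriptively on all treated patients.

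All of this stands as a limit on size. It leaves the conflict in wording in place and the group in the fourth row of the table exposed. The FAS denominator protects the reported ORR but not the count of five, because SAP 4.3.2 still ties that count to evaluable patients. The Synopsis also differs from 5.1 and 12.3.3 on the cut-off (two cycles plus a scan, against the first scan). This is minor, since the first scheduled scan falls at about Week 6, the end of Cycle 2.

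**Conclusion.** The point holds as a conflict over who enters the Simon count, with a possible rather than demonstrated rise in the false-go rate. The affected group is narrow: treated patients who leave for a non-safety reason, are not scanned, and are not coded as progression (or are coded as clinical progression, on the stricter reading).

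The rise from 0.182 to between 0.210 and 0.327 per cohort rests on four assumptions: d between 5 and 20%, all leavers non-responders, each one replaced, and 10% being an all-treated rate. The margin is thin, because the attained error starts at 0.182 and about one replacement per 31 uses it up.

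Scope is also limited. SAP 4.3.2 closed Cohort B after its 18 Stage 1 patients and applies no Simon design to Cohort C. The five-of-31 rule can run only in Cohort A, and only the Stage 1 count bears on Cohort B. A reader might combine the error over two cohorts, but that would describe the original plan only.

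**What to change.** Write one rule and use it in the Protocol Synopsis, 5.1, 12.2 and 12.3.3:

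- Count as a non-responder, without replacement, every treated expansion patient with centrally confirmed leiomyosarcoma who has no post-baseline scan because of death, clinical or symptomatic deterioration, a change in condition, or new anti-cancer therapy.
- Replace only patients whose histology is not confirmed centrally, or who leave for documented reasons unrelated to disease or treatment.
- Define *evaluable* to match in SAP 4.3.2, and add the population to SAP 6.7.
- State whether the 10% and 25% rates refer to all treated or to evaluable patients.

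This brings the Simon count closer to the SAP's all-treated ORR and takes the decision away from how a withdrawal is coded. If the rates are all-treated rates, the error returns to about 0.182 and power to 0.902.

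The cost is wording in both documents and a slightly lower evaluable ORR, with no extra patients. If the rates are evaluable-patient rates, power falls to about 0.874 with 5% leaving and 0.839 with 10% leaving.

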**12.3. Criteria for Evaluation****12.3.1. Safety**

All patients who receive at least dose of TTI-621 will be included in the safety analyses.

Adverse events, ECGs, LVEF assessments and laboratory data will be summarized and reviewed on an ongoing basis during the study. All adverse events, ECGs, LVEF assessments and safety laboratory abnormalities of potential clinical concern will be described. Safety data will be presented in tabular and/or graphical format and summarized descriptively by dose cohort and time where appropriate. Absolute value data and changes from baseline data will be summarized as appropriate.

AEs will be coded using the Medical Dictionary for Regulatory Activities (MedDRA) and severity of AEs and laboratory abnormalities will be graded using NCI CTCAE v5 as appropriate. Incidence tables of patients with AEs will be presented for all AEs by maximum severity, SAEs, AEs assessed as related to study drug and adverse events resulting in discontinuation of study drug.

For ECG analyses, the mean of the triplicate ECG parameters will be used as the observation for a patient at a nominal time point. Changes in ECG and laboratory measurements will be summarized.

Listings of all safety data sorted by dose cohort, patient and assessment date will be provided.

**12.3.2. CCI**

CCI [REDACTED] will be evaluated after single and multiple doses of TTI-621 during the course of the study. The CCI [REDACTED] of TTI-621, measured as CCI [REDACTED] [REDACTED], also will be investigated during the course of the study.

CCI [REDACTED] will be listed and summarized at each time point using descriptive statistics; graphical representations will also be provided. Analyses will be performed on the CCI [REDACTED] and will be outlined in the Statistical Analysis Plan.

Exploratory analyses may be conducted to evaluate the relationship between TTI-621 end-of-infusion and/or trough concentrations and various efficacy and safety endpoints.

CCI [REDACTED] from this study may be pooled with data from other studies and analyzed using population PK approaches. In addition, a model-based approach may be used to explore the potential relationship TTI-621 exposure metrics and efficacy, safety, and/or biomarker endpoints and reported separately.

The CCI [REDACTED] will be summarized descriptively. Exploratory analysis may be conducted to evaluate the possible effects of CCI [REDACTED] [REDACTED] efficacy and safety endpoints.

**12.3.3. Clinical Benefit**

Clinical efficacy will be evaluated by tumor response for patients with measurable disease as assessed by the Investigators using RECIST v1.1 (Appendix B). Duration of response will be calculated for patients who achieve a CR or PR and is defined as the time from the date of first documented response (CR or

PR) to the date of documented progression or death after achieving response. Disease control rate is defined as the percentage of patients who have achieved CR, PR, or SD lasting at least 12 weeks.

Clinical activity based on CCI [REDACTED] will be assessed as an CCI [REDACTED] of the study.

Patients enrolled in an expansion cohort who withdraw from the study prior to the first objective disease assessment for a reason other than disease progression or safety will be replaced in order to meet the statistical criteria for the Simon two-stage design; these patients will not be included in the response-evaluable population. For a patient enrolled into the dose expansion portion of the study based on local pathology that is not confirmed during central review, the patient must be replaced for purposes of meeting the statistical requirements of the study but may be allowed to continue on treatment after discussion with the Sponsor Medical Monitor.

For patients with asymptomatic progression only or suspected pseudoprogression, the patient may continue treatment beyond progression until a confirmation scan at least four weeks later has confirmed progression.

Efficacy analyses will be based on the efficacy analysis population, i.e. all patients who received at least one dose of study treatment, unless otherwise specified.

#### 12.3.4. Patient-Reported Outcomes

Patient-reported health-related quality of life will be assessed with the European Organisation for Research and Treatment of Cancer (EORTC) Quality-of-Life Questionnaire Core 30 (QLQ-C30) tool. The PRO measures will be collected on Day 1 of every cycle and at the End-of-Treatment visit. Paper versions of the questionnaire will be used. The questionnaire should be completed prior to initiation of study treatment. Whenever possible, if administration is not possible prior to all other procedures, every effort should be made to administer at the same time point in each visit. Patient-reported questionnaire should be completed by patients when a language translation is available in which the patient is fluent or literate.

Broadly used in cancer trials, validated, and available in over 80 different languages, the EORTC QLQ-C30 is a reliable and validated tool. The EORTC QLQ-C30 is a self-administered, self-reported general cancer-specific questionnaire consisting of 30 items covered by one of three dimensions:

- Global health status/ (two items)
- Functional scales (15 total items addressing either physical, role, emotional, cognitive or social functioning)
- Symptom scales (13 total items addressing either fatigue, nausea/vomiting, pain, dyspnea, insomnia, appetite loss, constipation, diarrhea, or financial impact)

The recall period is the past week and completion time is typically five to seven minutes. The questionnaire will be scored as described by the EORTC scoring manual.

**12.3.5. CCI**

[REDACTED]

[REDACTED]

[REDACTED]

